9.2.1 Treatment Assignment Procedures

We will randomly select one clinic (or more, as needed to meet the target sample size) within Michigan Medicine and Henry Ford Health System as the intervention clinic; PLWD in these clinics will receive the nudge intervention. PLWD within the other clinic in each system will serve as controls.

9.3 Interim analyses and Stopping Rules

No interim analyses are planned.

9.4 Outcomes

9.4.1 Primary outcome

The primary clinical outcome will be change in the total standardized daily dosage (TSDD) of the medication classes contributing to CNS polyRx as measured in the EHR, from baseline to 4 months after sending the adapted intervention.

9.4.2 Secondary outcomes

n/a

9.5 Data Analyses

- **Aim 1** will involve rapid and rigorous qualitative analysis. Focus group discussions and any follow-up phone calls will be audio recorded. Following transcription of focus groups, the transcripts will be used to create summaries for each focus group, which will then be reconciled through discussion. Summary data regarding tool refinement and recipient engagement will be transferred into a matrix for interpretation and comparison across groups. This matrix will be reviewed by all pilot investigators to select final refinements of the tool as well as to finalize the Aim 2 engagement strategy. If participants selected for a follow-up phone call agree to being recorded, the brief discussion will be audio recorded for accuracy purposes.
- **Aim 2:** With **N=120** PLWD, we expect to obtain a reasonably precise estimate of the first feasibility outcome, allowing us to determine the number of clinics within each health care system needed for the future ePCT.
- **Aim 3:** Four months after sending the tool, we will do a final EHR query (**Aim 3**) for all participants to assess the burden of CNS polyRx (i.e., total standardized daily dosage) and determine whether the prescribing regimen changed from the medications prescribed at baseline. We will use each active outpatient prescription for a CNS-active medication and convert them to a standardized daily dose using the minimal effective geriatric daily dose, adding the total across all CNS-active medications at the patient level. This—change in the total standardized daily dosage (TSDD) following the nudge intervention—will be the primary outcome for the study and subsequent trial. With the expected sample size of 120 PLWD (60 per group and 30 per clinic-group), we expect to have a good estimate of the variability of the distribution of change in TSSD (clinical outcome

measure) from baseline in each group as well as within-clinic correlation of the changes in TSSD.

Data analysis will be completed by a [name] team analyst, under supervision of the study biostatistician. Because the nature of the intervention is that any changes are made by the PLWD in consultation with their treating clinician, there are not trial results or information to provide to the clinician at completion of the pilot study (i.e., the intervention does not entail treatment changes other than those made by the treating clinician).

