Identifying and recruiting trial participants: Patients in Aim 2 and 3 will not be recruited directly to participate.

Eligibility and Ineligibility criteria: We will use the electronic health record (EHR) to identify patients living with dementia prescribed these problematic medication combinations (2a). Team data analysts will use DataDirect—the portal for researchers into the Michigan Medicine and HFHS EHRs—to identify PLWD seen in primary care with CNS-active polyRx. ICD-10 codes will be used to identify PLWD (including MCI) with an ambulatory care encounter with a primary care clinician (internal medicine, family medicine, or geriatrics) during the preceding 12 months. Within each system, we will identify a pair of clinics that have relatively similar panel characteristics (similar volume overall; PLWD with similar distributions of gender, race/ethnicity) to serve as the paired intervention-control sites. Among PLWD, we will use current outpatient medications data to identify those with ≥ 3 active prescriptions of the medications that contribute to CNS polyRx (e.g., antidepressants, antipsychotics, anti-epileptics, benzodiazepines, non-benzodiazepine benzodiazepine receptor agonist hypnotics, or opioids). We will contact the primary care clinicians of eligible PLWD once by email to offer them the opportunity to exclude potential PLWD participants for whom they think the intervention would be inappropriate; clinicians will have one week to opt potential participants out, or to suggest an eligible patient we may have missed (if they do not reply, we will assume that we can proceed).

Randomization: We will randomly select one clinic (or more, as needed to meet the target dyad sample size) within each system as the intervention clinic; dyads in these clinics will receive the nudge intervention. Dyads within the other clinic in each system will serve as controls.

Consent procedures: We will request a waiver of informed consent for PLWD participants in Aim 2 and 3. See section 11.2 for details.

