5 STUDY INTERVENTIONS

5.1 Interventions, Administration, and Duration

This project will adapt the EMPOWER educational brochure for PLWD receiving CNS polyRx. The educational brochure will be mailed to intervention participants identified through EHR at Michigan Medicine and Henry Ford Health System. Prior work utilizing the EMPOWER intervention specifically focused on sedative-hypnotic (e.g., benzodiazepines) deprescribing in older adults.¹⁵ In that EMPOWER trial, investigators developed an educational tool to “increase risk perception about benzodiazepines through knowledge acquisition and change in beliefs”¹⁶

(e.g., “*The dose that I am taking causes no side effects;*” [True/False]]); this tool (in the form of an 8-page brochure) was mailed to older adults on long-term benzodiazepine therapy. In the current study, this tool, to be delivered in the form of a brochure mailed to PLWD will describe what CNS polyRx is, present information about the associated risks, and suggest that they speak with their prescribing clinician or pharmacist about ways to potentially simplify their medication regimen. The tool will be adapted through three successive rounds of focus groups of PLWD and caregivers (n=5 PLWD-CP dyads per round for 15 dyads total). As part of Aim 2, we will identify eligible participants from the EHR and allow primary care clinicians to opt-out patients for whom they believe the intervention would be inappropriate. The educational tool will be mailed from the participating health systems with a cover letter from the respective clinic that includes the specific medication combination that made the PLWD eligible for the study. The goal of the educational nudge is to prompt a conversation with the PLWD’s clinician or pharmacist; the material will clearly state that individuals should not make any medication changes without discussing with their clinician. The EHR will be reviewed 4 months after the brochure is mailed to determine with there has been any change to the CNS polyRx.

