6.2.4 Completion/Final Evaluation

We will repeat a final EHR review for evidence of documented conversation related to these medications. In addition, we will review the active medications to determine the primary outcome of changes to the CNS-active medication regimen.

Additionally, we will conduct informant interviews with 10 primary care clinicians across intervention clinics from U-M and HFHS. The purpose of these interviews will be to explore potential barriers with experts and will explore whether:

- PLWD discussed receiving the tool with the clinician;
- Clinician perception of whether the tool motivated:
 - discussion related to prescribing that might not have occurred otherwise;
 - prescribing changes that might not have occurred otherwise;

- Clinician suggestions for modifications to the tool;
- Clinician suggestions regarding their perceived barriers or facilitators to improving the appropriateness of CNS-active prescribing, e.g.:
 - Clinical uncertainty regarding which medications to address;
 - Lack of access to clinical pharmacists to facilitate medication changes;
 - Lack of psychosocial resources for the PLWD-CP dyad.

7 **SAFETY ASSESSMENTS**

7.1 **Specification of Safety Parameters**

n/a

7.2 **Methods and Timing for Assessing, Recording, and Analyzing Safety Parameters**

The intervention is presenting education, which has a benign safety profile. Should the participants, in consultation with their clinician, choose to make medication changes, then participants should be at *lower* risk of adverse events by minimizing the burden of these medications. In a recent study of deprescribing among PLWD (of any, not limited by medication class), there was no difference in hospitalization or mortality rates in intervention groups, and review of records did not “reveal any pattern of adverse drug withdrawal events associated with the intervention.”¹⁷ In the original EMPOWER intervention (deprescribing of sedative-hypnotics), “no major adverse effects requiring hospitalization were reported.”¹⁵

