9 STATISTICAL CONSIDERATIONS

9.1 General Design Issues

For this nudge intervention, the primary clinical outcome will be change in the total standardized daily dosage (TSDD) of the medication classes contributing to CNS polyRx as measured in the EHR, from baseline to 4 months after sending the adapted intervention. We hypothesize a decline in the total standardized daily dosage (TSDD) following the nudge intervention. The presumed mechanism of the intervention is that the nudge educational tool will activate the dyad to discuss their current medication regimen with the prescribing clinician or a pharmacist. To determine whether the intervention has had this desired effect, as an implementation feasibility target, the team at each site will revisit intervention PLWD charts to complete an expedited chart review. We will complete initial reviews approximately two months after sending the tool and final review four months after sending the tool.

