9.2 Sample Size and Randomization

Our goal of participants is a total of 120 PLWD (a total of 60 across 2 intervention clinics; 60 across 2 control clinics), after allowing for clinician opt-out. This will then allow us to obtain a reasonably precise estimate of the first feasibility outcome (i.e., documentation of a prescribing-related conversation in the EHR), allowing us to determine the number of clinics within each health care system needed for the future ePCT. We will also be able to estimate the lower limit of a 95% confidence interval around the implementation feasibility target (i.e., documented discussion regarding CNS polyRx) not to drop below the pre-determined target of 50%. With N=60 PLWD (i.e., the PLWD in the intervention clinics) and assuming 65% to 75% to show evidence of CNS-medication discussions, the lower limits of a 95% confidence interval for implementation

feasibility target will be 51.6% to 62.1%, respectively. Meeting the implementation feasibility target will allow us to proceed to a full ePCT.

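### TSDD counts every prescription listed as active, so removing outdated entries at nudge-prompted contacts could show as a dose reduction, more often in the intervention arm

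*Combined protocol and SAP*

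**What the plan says.** Section 9.5 (Aim 3) defines the measure: "We will use each active outpatient prescription for a CNS-active medication and convert them to a standardized daily dose". Doses are scaled to a minimum effective geriatric dose and summed per patient. Section 6.2.4 describes the month-4 step the same way: "we will review the active medications to determine the primary outcome of changes to the CNS-active medication regimen". Eligibility rests on the same source. In section 4.3, "we will use current outpatient medications data to identify those with ≥ 3 active prescriptions".

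No section says what happens to expired, finished, duplicate or as-needed entries, and none sets an order-date, supply or fill condition. Section 10.1 lists the EHR data for Aims 2 and 3 as demographics, medications and mailing address. By contrast, section 2.1 defines CNS polyRx by more than 30 days of concurrent exposure.

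The mechanism is given in section 9.1: "the nudge educational tool will activate the dyad to discuss their current medication regimen with the prescribing clinician or a pharmacist". Under section 5.1, the clinic's cover letter "includes the specific medication combination that made the PLWD eligible for the study". Control patients are sent nothing.

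For the discussion review, section 9.1 says that "the team at each site will revisit intervention PLWD charts to complete an expedited chart review". Sections 6.2.3 and 6.2.4 also describe a review of notes for discussions, without naming an arm. No control discussion rate is therefore clearly planned.

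**The concern.** A medication list can hold entries that are no longer current, such as a finished course or an abandoned hypnotic. While such an entry is marked active it counts in full. When someone removes it, TSDD falls, although nothing was being prescribed under it.

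A change score with a control arm cancels this only if removal is equally frequent in both arms. Here the intervention is designed to produce the kind of contact at which a list is likely to be reviewed, and its letter names the recorded drugs. If a named drug is no longer taken, the letter points to that entry, in one arm only. Eligibility adds to this: an outdated entry helps a patient reach three active prescriptions, so selection may favour patients who have such entries.

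Section 9.5 makes TSDD change the primary outcome of this study and of the subsequent trial. It also expects the pilot to supply the variability of the change in each group and its within-clinic correlation. List cleaning would add to the spread of the changes. If reconciliation habits differ by clinic, it would also enter the correlation.

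**Working it through.** **The plan's own figure.** No figure is given for TSDD. The related figure is in section 9.2: "With N=60 PLWD (i.e., the PLWD in the intervention clinics) and assuming 65% to 75% to show evidence of CNS-medication discussions", with lower 95% limits of 51.6% and 62.1%. The exact (Clopper-Pearson) lower limit is the 2.5% quantile of Beta(x, n − x + 1):

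- x = 0.65 × 60 = 39: lower limit 51.6%
- x = 0.75 × 60 = 45: lower limit 62.1%

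Both reproduce. This confirms that 65% to 75% is the assumed discussion rate among the 60 intervention patients. It says nothing about outdated entries.

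**Which links are in the text.**

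| Link | Status |
|---|---|
| TSDD counts every active entry | Stated, section 9.5 |
| The nudge prompts regimen discussions | Stated, section 9.1 |
| Only intervention patients are prompted | Stated, sections 3 and 9.2.1 |
| Some active entries are outdated | Inferred |
| Some of these are removed at the discussions | Inferred |

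**Size if current prescribing does not change.** Let s be the share of baseline TSDD from outdated entries, r the probability that such an entry is removed at a discussion, and pI and pC the discussion rates in the intervention and control arms. Then

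spurious between-arm fall, as a share of baseline TSDD = s × r × (pI − pC).

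Inputs: pI = 65% to 75% (section 9.2). Assumed, with no source in the documents: s = 5% to 20%, r = 0.5 to 1, pC = 10% to 50%.

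| pI | pC | s = 5%, r = 0.5 | s = 10%, r = 1 | s = 20%, r = 1 |
|---|---|---|---|---|
| 65% | 50% | 0.4% | 1.5% | 3.0% |
| 65% | 30% | 0.9% | 3.5% | 7.0% |
| 65% | 10% | 1.4% | 5.5% | 11.0% |
| 75% | 50% | 0.6% | 2.5% | 5.0% |
| 75% | 30% | 1.1% | 4.5% | 9.0% |
| 75% | 10% | 1.6% | 6.5% | 13.0% |

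- Smallest: 0.05 × 0.5 × (0.65 − 0.50) = 0.00375, about 0.4%.
- Largest: 0.20 × 1 × (0.75 − 0.10) = 0.13, or 13%.
- The term is zero only if s = 0, r = 0 or pC = pI.

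The documents give no mean or standard deviation for TSDD, so these percentages cannot be converted to dose units or to a standardized effect.

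**The case against.** The strongest reply is that the decisive links are not in the documents. Nothing describes how either health system expires or reconciles entries, so both the presence of outdated entries and their removal are inferences. That stands, and it is why the size must be left open.

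Second, a reader might infer that the outcome is biased in favour of the nudge. The documents do not support a net direction. Section 7.3 anticipates patients changing medication without consulting a clinician. Such drugs may stay listed and hide real reductions. A prompted review could also add unrecorded drugs and raise TSDD. Nor do control lists stay untouched: usual care continues, and patients in both arms had a primary care encounter in the preceding 12 months (section 4.3).

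Third, a reader might infer that an inflated effect size is carried into the next trial, or that the decision to proceed is compromised. Neither follows. Section 9.5 specifies no between-arm TSDD estimate or test, and section 1.1 disclaims power. Progression under section 9.2 rests on the discussion target, judged by "the lower limit of a 95% confidence interval around the implementation feasibility target", and TSDD plays no part in it.

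Fourth, the outcome is prescribing as recorded, not intake. That is a legitimate choice, but an entry whose order lapsed before baseline is not current prescribing either.

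The existing safeguards do not close the gap. The clinician opt-out comes before mailing and asks about suitability. The check of the first 20 chart reviews (section 10.3.5) concerns abstraction accuracy. The clinician interviews ask about prescribing changes, not list currency.

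**Conclusion.** The point holds as a gap in the definition of the primary measure. With list status as the only test, TSDD cannot separate a prescription stopped after the nudge from an outdated entry removed because of it, and the trigger for removal differs by arm by design.

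The size is unknown. The illustrative range of about 0.4% to 13% of baseline TSDD rests on the plan's 65% to 75% discussion rate, on assumed values for s, r and pC, and on treating a documented discussion as the occasion for removal. It covers one component of error and is not an estimate of net bias.

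The consequence is limited to the piloted measure and to the variability and within-clinic correlation handed to the subsequent trial. It is worth settling now, because a redefinition after the pilot would leave those estimates describing a different measure.

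**What to change.** In section 9.5, extract order date, days' supply, refills and discontinuation date with the medication data. Compute TSDD in two ways, at baseline and month 4, in both arms:

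- **(a)** by list status, as now;
- **(b)** counting an entry only if it is active **and** its latest order covers the date, that is, up to order date + days' supply × (1 + refills) + a pre-specified grace period. The latest order for a drug supersedes earlier ones.

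The 1 in (1 + refills) is the first fill. Without it, an order with no refills would cover no days. Requiring active status as well keeps real discontinuations visible when refills remain. Entries without a usable local order keep list status in (b) and are flagged.

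Report the difference between (a) and (b) by arm as the list-cleaning component. Orders that lapse during follow-up but stay listed also enter that difference, with the opposite sign. The discontinuation date should therefore be used to show separately the dose from entries already uncovered at baseline and removed by month 4. Eligibility can stay on list status. Report how many patients have fewer than three counted prescriptions under (b).

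**Cost.** A few order fields from the same EHR query and some programming, with no patient contact. Measure (b) may drop slowly used as-needed drugs and orders with incomplete supply fields. It still counts an abandoned drug with refills left until that entry is removed. Keeping (a) alongside makes these effects visible.

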Aim 1: successive rounds of virtual focus groups conducted over Zoom to adapt the EMPOWER educational tool for people living with dementia (PLWD) receiving CNS polyRx and their care partners (CPs). Brief follow-up phone calls with select care partners who participated in the focus group discussion in order to reflect on and clarify any feedback and insight that emerged during the group discussion.

Aims 2 and 3: use the electronic health record (EHR) to identify a list of PLWD experiencing CNS polyRx and (b) a randomized-controlled clinical trial implementing the adapted EMPOWER intervention in two primary care clinics using pragmatic methods at University of Michigan Health and Henry Ford Health (n=120 PLWD). We will also interview prescribing clinicians to obtain their perspectives on barriers and facilitators to the intervention.

Interventions and Duration

Participants (i.e., PLWD experiencing CNS polyRx) will be mailed the educational tool. Four months after sending the tool, we will do a final EHR query for all participants to assess the burden of CNS polyRx (i.e., total standardized daily dosage) and determine whether the prescribing regimen changed from the medications prescribed at baseline. Participation will be over after the 4 months.

Sample Size and Population

Our goal is to include 4 participating clinics with at least 30 PLWDs with active CNS polyRx per clinic, for a total of about 120 eligible PLWDs.

STUDY TEAM ROSTER

Principal Investigator:

[name], MS

[name]

[name]

[contact]

[contact]

Main responsibilities/Key roles:

As the Principal Investigator, [name] will take primary responsibility for overall scientific direction and oversight of the project. [name] will: 1) lead the development of the educational tool for Aim 1; 2) work with Drs. [name] and [name] to oversee quantitative data collection and analysis for all aims, supported by data analyst; 3) work with [name] to oversee focus group and qualitative interviews and analysis, supported by study qualitative coordinator; 4) along with Co- Investigators, prepare research reports and manuscripts for peer-reviewed publication; 5) provide overall supervision of study staff.

Co-Investigators:

[name]

[name]

[name]

[contact]

[contact]

Main responsibilities/Key roles:

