3 STUDY DESIGN

- *Type/design of trial (e.g., placebo-controlled, double-mask, parallel design, open-label, dose escalation, dose-ranging)*

This is an educational nudge intervention with two intervention clinics and two control clinics.

- *Specific statement of the primary and secondary outcomes (must be consistent with Study Objectives)*

The primary clinical outcome will be change in the total standardized daily dosage (TSDD) of the medication classes contributing to CNS polyRx as measured in the EHR, from baseline to 4 months after sending the adapted intervention. We hypothesize that the TSDD of the medication classes contributing to CNS polyRx will decline from baseline to 4 months in participants receiving the nudge intervention (though this pilot study is not designed [or powered] to detect a statistically significant change).

Secondary Objectives are:

- a. Adapt a patient- oriented educational nudge intervention to help motivate CNS polyRx deprescribing among PLWD
- b. Establish mailing of the educational brochure within the clinic workflow by engaging clinicians and/or pharmacists at each of the participating clinics
- c. Establish implementation feasibility: after sending the tool, the proportion of enrollees with documentation in the EHR of discussion regarding CNS-active medications with a prescribing clinician (or pharmacist).

- *Study population and groups/arms including sample size (including a table, if appropriate)*

We will identify 120 PLWD experiencing CNS polyRx across participating clinics to receive the intervention.

- *Study location (e.g., in-patient or out-patient, clinic, community)*

A total of four primary care clinics at University of Michigan Health and Henry Ford Health; potentially more clinics will be engaged if necessary to reach the goal of N=120 PLWD.

- *Approximate duration of enrollment period and follow-up (specify individual participant vs. entire trial)*

Approximately 6 months accounting for EHR review, sending the nudge tool, and then allowing several months (4) afterwards for dyads to discuss with clinicians and make medication changes.

- *Description of intervention and administration*

An adapted EMPOWER brochure that will specifically be modified to address CNS polyRx (as opposed to the single-class focus of the original). The intervention will be adapted based

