on input from successive rounds of focus groups and then administered by mail through the clinic. There is no direct interaction between the study team and PLWD

- *Randomization, blinding and any stratification*

There is no patient-level randomization. Within each health system (University of Michigan and Henry Ford), we will randomly select one of the clinics where patients will receive the nudge intervention.

- *Other protocol specific details, such as centralization of evaluations (e.g., central laboratory or central reading center for clinical scans).*

n/a

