4.2 Exclusion Criteria

Aim 1: Focus Group Research

The exclusion criteria for PLWD will be:

- (1) Individuals who do not read, speak, or understand English;
- (2) Individuals with a diagnosis of dementia that is in severe stage;
- (3) Individuals with visual impairment that would prohibit viewing study materials;

(4) Individuals with hearing impairment sufficient to prohibit participation in a focus group.

The exclusion criteria for CPs will be:

- (1) Individuals who do not read, speak or understand English;
- (2) Individuals with any visual impairment that would prohibit viewing study materials;
- (3) Individuals with any hearing impairment that would prohibit participation in a focus group.

Aim 2 and 3: Intervention

(4) After identifying potential participants through EHR at the intervention and control clinics, we will provide the list to their primary care clinicians to review and opt-out potential participants for whom they feel the intervention is not appropriate. (While the control clinics will *not* receive the intervention, we will still allow their clinicians to indicate PLWD for whom they think the intervention would be inappropriate in order to have the most comparable groups.) At intervention sites, clinicians will also be given the opportunity to suggest any additional patients at the clinic who meet the inclusion criteria and may have been missed by the EHR search. The opt out letter and responses will be sent by email to/from the research assistant or coordinator at each respective site and the clinic liaison. If doctors wish to suggest any additional patients, those patients will be added to REDCap by the health system's own research team. Patients selected in this way will be noted in REDCap as having been selected through this alternate method.

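### Section 9.5 expects a good estimate of the within-clinic correlation of TSDD change, but four clinics are too few to give one (minor)

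*Combined protocol and SAP*

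**What the plan says.** The Précis (Sample Size and Population) aims for "4 participating clinics with at least 30 PLWDs with active CNS polyRx per clinic". Section 9.2 splits the 120 into 60 across two intervention clinics and 60 across two control clinics. On allocation, Section 3 says: "Within each health system (University of Michigan and Henry Ford), we will randomly select one of the clinics" to receive the intervention. Section 3 also says that "potentially more clinics will be engaged if necessary to reach the goal of N=120 PLWD".

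The precision statement is in Section 9.5, Aim 3. It opens "With the expected sample size of 120 PLWD (60 per group and 30 per clinic-group" and goes on to expect a good estimate of the variability of the change "in each group as well as within-clinic correlation of the changes in TSSD" (TSSD there is evidently TSDD). It gives no assumed ICC, target width, estimator or model. The same paragraph says that change in TSDD "will be the primary outcome for the study and subsequent trial".

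Sections 1.1 and 3 say that the pilot is not powered to detect a significant change in TSDD. That caveat concerns a test of the outcome and does not qualify the statement about the correlation.

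**The concern.** The sentence treats 120 patients as the sample size for two different quantities. For the patient-level spread of TSDD change, the number of patients is roughly the right thing to count. For the within-clinic correlation, the information lies mainly in how far the clinic means differ, and there are only four of them. More patients per clinic sharpen each mean but do not add clinics.

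What is at stake is how the result will be read. TSDD change is to be the primary outcome of the later trial, so a reader of Section 9.5 could take the pilot ICC as a dependable planning value. A chance estimate at or below zero would then look like evidence that clustering can be ignored.

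**Working it through.** **The plan's own figures.** None is given for the ICC. The only computed precision figures in the document are the lower 95% limits in Section 9.2 for the documented-discussion proportion: 51.6% and 62.1% at 65% and 75% of 60. Exact Clopper-Pearson limits for 39/60 and 45/60 are 51.6% and 62.1%, so those figures reproduce. No such calculation supports the ICC statement.

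**Inputs.** There are k = 4 clinics of m = 30 (Précis, 9.2, 9.5), two per arm, randomised within two health systems (Section 3). The ICC is not in the documents; 0.01, 0.05 and 0.10 are assumed. The formulas assume normal data and equal clinic sizes.

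**Degrees of freedom.** Within clinics: 4 × 29 = 116. Between clinics: 4 - 1 = 3, or 2 after fitting arm. Fitting health system as well would leave 1, but no section specifies that model.

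**Interval for an observed ICC r.** One-way ANOVA gives F = 1 + m·r/(1 - r). Each limit is (F/q - 1)/(F/q + m - 1), where q is the 97.5% quantile (lower limit) or the 2.5% quantile (upper limit) of the F distribution.

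For r = 0.05, F = 1 + 30 × 0.05/0.95 = 2.579.

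- 3 df: quantiles 3.231 and 0.0717, so F/q = 0.798 and 35.97. Limits: (0.798 - 1)/(0.798 + 29) = -0.007 and (35.97 - 1)/(35.97 + 29) = 0.54.
- 2 df: quantiles 3.809 and 0.0253, so F/q = 0.677 and 101.8. Limits: -0.011 and 0.77.

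Results over the assumed range:

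| Observed ICC | 3 df | 2 df (arm fitted) |
|---|---|---|
| 0.01 | -0.020 to 0.36 | -0.022 to 0.63 |
| 0.05 | -0.007 to 0.54 | -0.011 to 0.77 |
| 0.10 | 0.011 to 0.66 | 0.005 to 0.85 |

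As a design effect at 30 per clinic, the most favourable case for 0.05 (3 df) spans about 1 to 1 + 29 × 0.538 = 16.6, taking the negative lower limit as zero.

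**Chance of an estimate at or below zero.** With true ICC 0.05, θ = 2.579, and the estimate is zero or negative when an F variable falls below 1/θ = 0.388. The probability is 0.238 (3 df) or 0.320 (2 df). The central 95% sampling range of the estimate is -0.03 to 0.20 (3 df) or 0.23 (2 df).

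**More clinics within N = 120.** Observed ICC 0.05, arm fitted:

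- 6 × 20 (4 and 114 df): F = 2.053, interval -0.015 to 0.45.
- 8 × 15 (6 and 112 df): F = 1.789, interval -0.020 to 0.34.

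**Robustness.** Section 4.2 makes unequal clinic sizes possible: clinicians may opt patients out, and at intervention sites "clinicians will also be given the opportunity to suggest any additional patients at the clinic who meet the inclusion criteria". In simulation with arm fitted and true ICC 0.05, clinic sizes of 20 and 40 in each arm give a zero or negative estimate 34% of the time, and 15 and 45 give 37%, against 32% for equal sizes. A skewed outcome (assumed: 70% no change, 30% exponential decline) gives 31%, with 93.8% coverage of the interval. Neither alters the conclusion.

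**The variability half of the sentence.** The ordinary SD of 60 patients in two clinics of 30, simulated with normal data, has a central 95% range relative to the true SD of 0.82 to 1.18 at ICC 0.01, 0.81 to 1.17 at 0.05 and 0.79 to 1.17 at 0.10. That is reasonable precision for a pilot.

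**The case against.** The best defence is that this is a pilot and that a good estimate is a qualitative phrase with no printed width to contradict. That is fair as far as it goes: the sentence is an unsupported expectation, not a wrong number. But an interval from no clustering to more than half of the total variance is not good on any ordinary reading, and reporting an ICC does not require promising that it will be precise.

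The imprecision also looks less dramatic as a sampling range than as a confidence interval. At a true ICC of 0.01 the estimate would fall between -0.03 and 0.10 (3 df) or 0.12 (2 df) in 95% of pilots. That is true, but it still does not separate negligible from substantial clustering.

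Three stronger readings are tempting, and the documents support none of them.

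- A reader might infer that the variability claim fails too, because each arm has only two clinics. Section 9.5 promises the spread of patient-level change, not the SD of clinic means, and at small ICCs that spread is estimated adequately. An interval that allowed for any ICC would be wider.
- A reader might quote the 1-df case, where the upper limit at an observed ICC of 0.05 is 0.99. That requires fitting health system as well as arm, which no section specifies.
- A reader might conclude that the later trial will be mis-sized. Sections 9.2 and 9.5 tie the number of future clinics to the feasibility outcome and never say that the pilot ICC will be used.

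**Conclusion.** The point stands for the within-clinic correlation only. Section 9.5 attributes to the design a precision that four clinics do not provide, and the conclusion is the same for 3 or 2 df and for each assumed ICC from 0.01 to 0.10. The sizes quoted rest on assumed ICCs, normal data and equal clinics; the checks on the last two leave the conclusion unchanged.

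Severity is minor. No pilot decision uses the ICC: the go-ahead criterion in Section 9.2 is the documented-discussion target, where meeting the "feasibility target will allow us to proceed to a full ePCT". Harm would arise only if someone later took the point estimate without its interval, and that use is an inference.

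**What to change.** In Section 9.5 (Aim 3), remove the within-clinic correlation from the good-estimate sentence and leave the statement on variability in each group as it is. Add one sentence, for example: the ICC of TSDD change will be reported descriptively with its 95% confidence interval and, because there are only about four clinics, it is too imprecise to serve alone as a planning value.

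This needs no extra patients, clinics or data. The cost is that one stated deliverable of the pilot becomes less favourable. How a later trial should be sized is outside this protocol and need not be settled here.
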